Study Title: Storytelling Narrative Communication Intervention for Smoking Cessation in Women Living with HIV

NCT Number: NCT03289676

Date: 01/10/2018

University of Massachusetts Boston Institutional Review Board Protocol

A. Title: Storytelling Narrative Communication Intervention for Smoking Cessation in Women Living with HIV

B. Investigators: [name], RN, University of Massachusetts Boston
 [name], RN, FAAN, Dana-Farber/Harvard Cancer Center
 [name], RN, APHN-BC, FAAN, University of Massachusetts Boston

PROJECT DESCRIPTION

HIV has transformed into a chronic illness due to the advent of effective treatments in the absence of a cure. As a result, the prevalence of non-AIDS defining cancers (NADCs), including lung cancer, has increased three-fold among people living with HIV. NADCs now account for 50% of all cancers among the people. Smoking is one of the major contributing factors to lung cancer and smoking prevalence is substantially higher in this population than the general U.S. population. Smoking prevalence does not differ by gender among people living with HIV. Women of color, particularly African American women represent the majority of women living with HIV (WLHIV) followed by Latinas. WLHIV smoke at a rate almost 3 times higher than that for the general U.S. female population (e.g., 42% vs. 16%). The proposed study has two phases: 1) the development of a storytelling narrative communication (SNC) intervention that will be added to an established HIV-tailored smoking cessation intervention and 2) a two-arm randomized controlled trial (RCT) of the HIV-tailored intervention plus the SNC Intervention compared with the HIV-tailored intervention only. We will develop narrative videos with three to five WLHIV who will be talking about their personal struggles with smoking and success in quitting. Our preliminary study revealed that the established HIV-tailored intervention was effective only for short-term (≤ 2 months) abstinence. Many relapsed to smoking between the 2nd and 6th month of quitting. We propose that the SNC intervention will be an effective strategy to sustain their quit efforts for long-term abstinence (≥ 6 months). A total of 60 WLHIV will be recruited and randomly assigned to either the experimental arm (a combination of HIV-tailored and SNC interventions) or the control arm (HIV-tailored intervention only).

STUDY AIMS

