- Phase 1. Development of Narrative Video:** We will first develop narrative videos in collaboration with community organizations of WLHIV in Boston. The video will be filmed in person at the University of Massachusetts Boston.
- Phase 2. A Randomized Controlled Trial (RCT) of a Story Telling Narrative Communication Intervention:** We will conduct a two-arm RCT assigning participants at a ratio of 1:1 to either one of the two arms (**Experimental:** HIV-tailored plus SNC interventions vs. **Control:** HIV-tailored plus attention-control interventions). Both arms will have eight weekly sessions of a 30-minute HIV-tailored cessation intervention (cognitive behavioral therapy plus nicotine patches). The experimental arm will receive three 5-minute SNC videos (testimonial stories about successful quitting), each per month between the first and third month of quitting, whereas the control arm receive three 5-minute attention control videos (women talking about being diagnosed with HIV) at the same monthly interval. However, participants in the control arm will also receive the SNC videos talking about successful stories of smoking cessation right after the last follow-up assessment (3-month follow-up post-quit). The overall flow of the study is illustrated in Figure 1. All research-related procedures will be conducted remotely.

Figure 1. The overall design of the study

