8. Have at least eight full drops of saliva drip from the tube onto the white padded area of the test strip (right below the three green arrows).

A research staff member will closely monitor the whole process via the video call. She/he will be blind to treatment condition. The person can read the result of the test when the blue line on top of the strip disappears, which usually takes 20-30 minutes. She/he will ask participants to take a photo of the strip right after the video call and send it to her/him. Then, the person will share the photo with other research staff to validate one's reading of the result.

Study Measures and Assessment Procedures: Baseline and three follow-up assessments will be conducted by telephone survey. All measures (see Table 1 below) have been tested and validated for use with WLHIV. Those who report abstinence will receive NicAlert® test kits at 3-month follow-up by a post office mail right before the follow-up assessments. As described above, participants will be guided step-by-step to perform the test while the whole process being closely monitored by research staff via a video call.

Table 1 Assessment schedule of study measures

Variables	Measure	Base	1M*	2 Ms*	3 Ms*
Demographics	Demographic Datasheet	✓			
History of HIV Infection	Year of the diagnosis, CD4 cell count, and viral load	✓			
HIV-medication Adherence	CASE Medication Adherence Scale ⁴⁰	✓			
History of Smoking and Quitting	Smoking and Quitting Datasheet	✓			
Stigma and Secrecy	HIV-related Stigma Scale ⁴¹	✓			
Alcohol Use	Alcohol Use Disorders Identification Test (AUDIT) ³²	✓			
Depression	Patient Health Questionnaire-9 ⁴²	✓			✓
Anxiety	Generalized Anxiety Scale-7 ⁴³	✓			✓
Nicotine Dependence	Fagerström Test for Nicotine Dependence ^{37,38}	✓	✓	✓	✓
Self-Efficacy	Self-Efficacy Scale ⁴⁴	✓	✓	✓	✓
Nicotine Withdrawal	Minnesota Tobacco Withdrawal Scale ³⁶		✓	✓	✓
Narrative Engagement	The Measure of Narrative Engagement ¹⁹			✓	✓
Program Evaluation	The Client Satisfaction Questionnaire ⁴⁵		✓	✓	✓
Abstinence or Cigarette Consumption	7-day Timeline Follow-back Smoking Behavior ³⁵		✓	✓	✓
	Saliva Cotinine Test (NicAlert®)				✓
Treatment Fidelity	Intervention Fidelity and Competence Scale ([name], unpublished work)		✓	✓	✓

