Power and Sample Size: This study aims to establish a preliminary effect size. In the currently ongoing study, abstinence rate for the video arm was 75.5% at post-quit 1 month but dropped to 20.0% at post-quit 3 months. For a two-sided test at a 5% significance level, 52 participants are required per arm to have 80% of power for abstinence rates 45.5% vs. 20%.⁴⁶ As a pilot study, we will recruit 50 subjects (25 per arm).

Data Analysis: Data analysis will be done in collaboration with the **U54 Research Design and Analysis Core**. Prior to data entry, data will be reviewed and double-checked for completeness and coding errors first by a research assistant and then by a data manager. An intention-to-treat analysis strategy will be used for cessation outcomes with missing values.

Specific Aim 1: Identify storytelling narrative communication (SNC) intervention components that are rated high in transport and identification* for use as an enhancement to an HIV-tailored smoking cessation intervention (*Narrative Understanding, Attentional Focus, Narrative Presence, and Emotional Engagement). Through two local networks of Black WLHIV in which [name] is a key collaborator, we will identify volunteers who have quit smoking and film them while they tell their story of quitting. We will ask them structured questions based on Bandura's Self-Efficacy Model to elicit the story components. When the film is edited effectively for clarity of content and length, it will be tested for acceptability using a mix-methods approach. Using focus groups the film will be shown and participants will be asked what they liked the most and the least about the film. These data will be analyzed for saturation through thematic analyses.

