Specific Aim 2: Determine the feasibility and acceptability of an SNC intervention for smoking cessation for WLHIV by assessing 1) the rate of **recruitment and retention** for feasibility and 2) the degree of **transport and identification** for acceptability in the narrative enhancement. We will identify and describe the time to recruitment and any barriers. We will also describe reasons for study refusal and compare refusal rates by age ranges and number of cigarettes smoked per day, using χ^2 and t-tests. We will compare attrition rates at each follow-up by intervention condition and abstinence status, using Mann-Whitney tests. Subjects will complete an Exit Survey, rating their overall satisfaction with the intervention that they have. They will also rate their experience with the SNC videos, using a 7-point Likert-type scale.⁴⁵ In addition, the Measure of Narrative Engagement will be used as a quantitative indicator of 1) narrative understanding, 2) attentional focus, 3) narrative presence, and 4) emotional engagement.¹⁹

Specific Aim 3: Establish an effect size of HIV-tailored smoking cessation and SNC interventions in comparison with the HIV-tailored smoking cessation intervention only for WLHIV by comparing 30-day abstinence rates at 6-month follow-up. We will evaluate the balance of baseline demographics and smoking behavior between the two arms, using t-tests or Mann-Whitney tests for continuous variables and χ^2 tests for categorical variables. We will examine differences in continuous or 7-day point-prevalence abstinence rates between the two arms, using the χ^2 tests. Individuals who are not available at follow-up assessments or yield a cotinine test result higher than the cutoff level of 0 (cotinine level 0-30mg/ml) will be all treated as smoking. We will calculate an effect size by comparing 30-day abstinence rates at 6-month follow-up point between the two arms. We will also explore longitudinal logistic regression models under the framework of generalized linear mixed models to examine the relationships between abstinence status and intervention conditions over time.

PROTECTION OF HUMAN SUBJECTS

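### No analysis of abstinence names a baseline covariate, although at 25 per arm one pre-specified adjustment would cheaply protect the effect size against chance imbalance

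*Protocol*

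**What the plan says.** The Aim 3 text is the same in the Protocol (Data Analysis) and in the SAP. It begins "We will evaluate the balance of baseline demographics and smoking behavior between the two arms", using t-tests, Mann-Whitney tests and chi-square tests. Nothing says what follows if a difference is found. It continues "We will examine differences in continuous or 7-day point-prevalence abstinence rates between the two arms", by chi-square. The effect size is a direct comparison of 30-day abstinence rates at 6 months. The only regression is an exploratory generalised linear mixed model relating abstinence to intervention condition over time, with no covariates listed.

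Allocation is described as "assigning participants at a ratio of 1:1 to either one of the two arms", with no stratification, blocking or minimisation mentioned.

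Suitable covariates are already collected. Table 1 schedules the "Fagerström Test for Nicotine Dependence" at baseline and again at each follow-up, and the screening script asks for average daily cigarettes. The nicotine replacement section also uses both quantities in deciding which products a participant is sent.

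On size, Power and Sample Size says "For a two-sided test at a 5% significance level, 52 participants are required per arm" "to have 80% of power for abstinence rates 45.5% vs. 20"%, and then "As a pilot study, we will recruit 50 subjects (25 per arm").

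**The concern.** The stated product of Aim 3 is an effect size for later grant applications. In a two-arm trial of this size, the arms can differ by chance on how dependent the women are. If dependence predicts quitting, that difference passes straight into the estimated effect and from there into the next trial's sample size.

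The balance tests do not protect against this. After a sound randomisation any baseline difference is chance, so the test answers no open question, and no action depends on it. It also leaves room to choose covariates after the results are seen.

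**Working it through.** **1. The plan's own figure.** Inputs from Power and Sample Size: p1 = 0.455, p2 = 0.20, two-sided 5%, 80% power. Pooled formula, with mean rate (0.455 + 0.20)/2 = 0.3275:

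n = [1.96·√(2·0.3275·0.6725) + 0.8416·√(0.455·0.545 + 0.20·0.80)]² / 0.255² = (1.301 + 0.538)² / 0.0650 ≈ 52 per arm.

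This reproduces the stated 52.

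**2. Precision at the planned size.** SE of the difference at 25 per arm = √[(0.2480 + 0.1600)/25] = 0.128. The 95% half-width is 1.96 × 0.128 ≈ 25 points, against a planned difference of 25.5 points.

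**3. How often imbalance occurs.** Under simple 1:1 randomisation the standardised difference in a baseline covariate has SD √(2/25) = 0.283.
- Above 0.3 SD in either direction: z = 0.3/0.283 = 1.06, probability about 29%.
- Above 0.5 SD: z = 0.5/0.283 = 1.77, probability about 8%.

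A balance test at 5% flags only differences above about 1.96 × 0.283 = 0.55 SD, so an observed 0.5 SD imbalance would be reported as non-significant.

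**4. What a 0.5 SD imbalance does.** The documents give no association between dependence and abstinence, so its strength is assumed as an odds ratio (OR) of abstinence per SD of higher dependence. To first order the shift is |ln OR| × mean p(1−p) × 0.5, with mean p(1−p) = (0.248 + 0.160)/2 = 0.204. The simulation used 25 per arm, 45.5% vs 20%, a standard-normal covariate and several thousand trials per setting. It compared the unadjusted difference with a standardised risk difference from a logistic model.

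| OR per SD (assumed) | First-order shift, points | Simulated shift, unadjusted, points |
|---|---|---|
| 0.8 | 0.223 × 0.204 × 0.5 = 2.3 | about 2 |
| 0.67 | 0.400 × 0.204 × 0.5 = 4.1 | about 4 |
| 0.5 | 0.693 × 0.204 × 0.5 = 7.1 | 6–7 |
| 0.4 | 0.916 × 0.204 × 0.5 = 9.3 | 8–9 |

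After adjustment the remaining shift was under 1 point in each setting. The first-order formula slightly overstates the effect of a strong covariate.

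**5. Precision gained.** Simulated SD of the risk difference, unadjusted to adjusted:
- OR 0.8: 0.125 to 0.126, no gain.
- OR 0.67: 0.126 to 0.125, negligible.
- OR 0.5: 0.129 to 0.124, so the half-width falls by 1.96 × 0.005, about 1 point.
- OR 0.4: 0.127 to 0.117, so the half-width falls by 1.96 × 0.010, about 2 points.

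With no association at all, the variance rises by about 1–2%.

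**6. Power and type I error.** Exact enumeration of the unadjusted chi-square test at 25 per arm gives power 0.51. This does not depend on the covariate when the marginal rates are fixed. The adjusted likelihood-ratio test gives about 0.55 (OR 0.5) to 0.56 (OR 0.4). Its type I error at a 30% null rate was roughly 5–6%, so part of the small gain may be a slightly liberal test.

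**7. How many covariates the data can carry.** Expected abstainers are 25 × 0.455 + 25 × 0.20 = 11.4 + 5.0 ≈ 16 under the planned effect, and 50 × 0.20 = 10 if both arms are at 20%. With arm and one covariate that is about 8 or 5 events per coefficient, so one covariate is the limit.

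**8. Sensitivity to the total.** The Project Description instead says "A total of 60 WLHIV will be recruited and randomly assigned". At 30 per arm the SD of the imbalance is √(2/30) = 0.26 rather than 0.28, and the conclusion is unchanged.

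**The case against.** The case for leaving the plan alone is reasonable. The unadjusted difference is unbiased over randomisation, and its confidence interval already allows for chance imbalance. The study is a declared pilot, so power is not its criterion. Sampling error of about ±25 points outweighs any shift in the table above. The benefit rests on a prognostic strength that the documents do not give, and the larger shifts need both a strong covariate and an imbalance seen in about 8% of trials. All of this stands, and it limits the size of the point. It does not remove the point, because the covariate is already collected and the cost is close to nil.

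A reader might infer more, in three ways that the documents do not support:
- That the plan rules out adjustment. It does not: the mixed model's covariates are unspecified, not excluded.
- That the planned estimate is biased. Only the estimate conditional on an observed imbalance is shifted, and randomisation averages this out.
- That a shift of 7 to 9 points is to be expected. That is the strong end of an assumed range; at OR 0.8 the shift is about 2 points and precision does not improve.

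**Conclusion.** The omission is real and identical in both documents: baseline balance is tested to no purpose, and no covariate is named in any analysis of abstinence. Its consequence is modest. A 0.5 SD imbalance, exceeded in about 8% of trials, would move the estimated difference by about 2 to 9 points over the assumed range of OR 0.8 to 0.4 per SD, and one adjustment removes nearly all of it. The precision gain runs from nil to about 2 points off a half-width of about 25. These figures assume simple 1:1 randomisation, 25 per arm, rates of 45.5% and 20%, and a covariate acting linearly on the log-odds scale. This is a worthwhile, low-cost improvement and not a flaw that invalidates the comparison. It should not be presented as a remedy for low power.

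**What to change.** In Aim 3 of both documents:
- Keep the chi-square test and the unadjusted difference in rates.
- Pre-specify one covariate, the baseline Fagerström score. Table 1 also measures it at follow-up, so state that only the baseline value is used. Report beside the unadjusted result a standardised risk difference with 95% CI from a logistic model with arm and that score.
- Apply this to the abstinence outcome that defines the effect size, once that is settled. Aim 3 uses 30-day abstinence at 6 months, whereas Table 1 ends at 3 months with a 7-day measure, so definition and time point must be reconciled first.
- Include the same covariate in the mixed model.
- State that the unadjusted difference stands alone if the logistic model does not converge.
- Replace the baseline p-values with a descriptive table by arm.

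This costs a few sentences of text and needs no new data, visits or participants. The downside is a slight loss of precision if the score turns out not to predict abstinence. With about 10 to 16 abstainers expected, no second covariate should be added.

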The Purposes of the study are to 1) Identify SNC intervention components that are rated high in transport and identification for use as an enhancement to an HIV-tailored smoking cessation intervention; 2) Determine the feasibility and acceptability of the SNC intervention for WLHIV by assessing the rate of recruitment and retention for feasibility and the degree of transport and identification for acceptability; and 3) Establish an effect size of HIV-tailored and SNC interventions for smoking cessation in comparison with the HIV-tailored smoking cessation intervention only for WLHIV, for subsequent grant applications.

SIGNIFICANCE OF THE STUDY

People living with HIV now live longer because of the use of highly active antiretroviral therapy.¹⁻³ However, the burden of non-AIDS related, especially, non-AIDS defining cancers (NADCs) has increased considerably and smoking is a profound cause of NADCs.³⁻⁶ These cancers now account for 50% of all cancers among those with HIV, with lung cancer being the most common and deadliest cancer.⁶ People living with HIV smoke cigarettes at much higher rates than the general U.S. population i.e., 40-80% versus 19%.^{1,7-9} There is no gender difference in smoking prevalence among people living with HIV. Women living with HIV (WLHIV) smoke at a rate almost three times higher than that for the general U.S. female population.⁹ Given the strong association between smoking and the development of lung cancer, smoking cessation interventions that are tailored to the group are critical to decrease the morbidity and mortality associated with lung cancer.

Women of color, particularly, African American women in the United States represent the majority of WLHIV followed by Latinas.¹⁰ Blacks bear a disproportionate share of cancer burden, having the highest death rate and shortest survival of any racial or ethnic group for most cancers.¹¹⁻¹³ Five-year relative survival is lower for Blacks than for Whites in most cancers at each stage of diagnosis.¹¹ The majority of participants in smoking

cessation studies for people living with HIV were males (> 80%) and studies conducted with WLHIV are very scarce.¹⁴ Compared to men, women face more barriers to seeking treatment, including transportation and childcare issues.¹⁵ A smoking cessation intervention that can be accessible at home may be an alternative strategies to reach WLHIV.

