**Specific Aim 2:** Determine the feasibility and acceptability of an SNC intervention for smoking cessation for WLHIV by assessing 1) the rate of **recruitment** and **retention** for feasibility and 2) the degree of **transport** and **identification** for acceptability in the narrative enhancement. We will identify and describe the time to recruitment and any barriers. We will also describe reasons for study refusal and compare refusal rates by age ranges and number of cigarettes smoked per day, using  $\chi^2$  and t-tests. We will compare attrition rates at each follow-up by intervention condition and abstinence status, using Mann-Whitney tests. Subjects will complete an Exit Survey, rating their overall satisfaction with the intervention that they have. They will also rate their experience with the SNC videos, using a 7-point Likert-type scale. In addition, the Measure of Narrative Engagement will be used as a quantitative indicator of 1) narrative understanding, 2) attentional focus, 3) narrative presence, and 4) emotional engagement.

**Specific Aim 3:** Establish an effect size of HIV-tailored smoking cessation and SNC interventions in comparison with the HIV-tailored smoking cessation intervention only for WLHIV by comparing 30-day abstinence rates at 6-month follow-up. We will evaluate the balance of baseline demographics and smoking behavior between the two arms, using t-tests or Mann-Whitney tests for continuous variables and  $\chi^2$  tests for categorical variables. We will examine differences in continuous or 7-day point-prevalence abstinence rates between the two arms, using the  $\chi^2$  tests. Individuals who are not available at follow-up assessments or yield a cotinine test result higher than the cutoff level of 0 (cotinine level 0-30mg/ml) will be all treated as smoking. We will calculate an effect size by comparing 30-day abstinence rates at 6-month follow-up point between the two arms. We will also explore longitudinal logistic regression models under the framework of generalized linear mixed models to examine the relationships between abstinence status and intervention conditions over time.

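### The effect size rests on coding every absent woman as smoking, with no alternative handling of missing abstinence, so it mixes cessation with retention

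*Protocol*

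**What the plan says.** Under Data Analysis, the protocol makes one general statement: "An intention-to-treat analysis strategy will be used for cessation outcomes with missing values". Specific Aim 3, worded alike in protocol and SAP, supplies the rule. It covers "Individuals who are not available at follow-up assessments or yield a cotinine test result higher than the cutoff level of 0", and the SAP says that they "will be all treated as smoking". No completers analysis, imputation or bounding analysis of abstinence is named, and no dropout rate is assumed.

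The effect size is a main product of the study. The protocol's Study Aims want it "for subsequent grant applications", and Specific Aim 3 defines it: "We will calculate an effect size by comparing 30-day abstinence rates at 6-month follow-up point between the two arms".

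Two other planned analyses bear on the point. Specific Aim 2 compares attrition at each follow-up by arm and by abstinence status. Specific Aim 3 explores a longitudinal logistic mixed model, without saying how missed visits enter it.

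**The concern.** Counting the absent as smokers is often defended as conservative. That holds for the abstinence rate within one arm. It does not hold for a difference between arms, because each arm is marked down in proportion to its own losses. A difference in retention can then pass for a difference in cessation, or hide one.

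This matters more here than in a trial whose product is a test result. The size of the difference is what gets carried forward, and with 25 women per arm a few more losses on one side will move it. Aim 2 will show whether attrition differed, but nothing in the plan takes that finding into the effect size. A later trial with different retention could then be planned on a figure that partly reflects this study's dropout.

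**Working it through.** **Inputs from the protocol (Power and Sample Size).** Planning rates are 45.5% v 20%, with two-sided 5% significance, 80% power and 25 women per arm. (The Project Description gives a total of 60; 25 per arm is used here.)

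**Inputs assumed.** The documents give no attrition figure. The scenarios use 3 of 25 (12%) and 7 of 25 (28%) lost, or 20% lost in both arms. The 30% abstinence rate in one null scenario is also an assumption.

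**Step 1: the plan's own figure.** The protocol states: "For a two-sided test at a 5% significance level, 52 participants are required per arm", for "80% of power for abstinence rates 45.5% vs. 20" per cent. The pooled-variance formula for two proportions is

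n = [1.96 √(2p̄(1−p̄)) + 0.842 √(p₁(1−p₁) + p₂(1−p₂))]² / (p₁−p₂)².

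With p̄ = 0.3275 this is (1.301 + 0.538)² / 0.255² = 51.97, so 52 per arm. The figure reproduces, and it contains no allowance for dropout.

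**Step 2: what the rule does to a rate.** Let p be the true abstinence rate, d the share lost and q the share of absent women who are abstinent. The coded rate is p − d·q. If absence is unrelated to smoking, q = p and the coded rate is p(1 − d). If all absent women smoke, q = 0 and the coded rate is correct.

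**Step 3: no true effect, absence unrelated to smoking.**

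| True rate, both arms | Lost, SNC v control | Coded rates | Coded difference |
|---|---|---|---|
| 20% | equal, any level | equal | 0 |
| 20% | 3 v 7 of 25 | 0.20 × 0.88 = 17.6% v 0.20 × 0.72 = 14.4% | +3.2 points |
| 30% (assumed) | 3 v 7 of 25 | 0.30 × 0.88 = 26.4% v 0.30 × 0.72 = 21.6% | +4.8 points |

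Swapping the losses between the arms reverses the sign.

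**Step 4: planning rates true, absence unrelated to smoking.**

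| Lost, SNC / control | Coded difference |
|---|---|
| none | 45.5 − 20.0 = 25.5 points |
| 20% / 20% | 36.4 − 16.0 = 20.4 points |
| 12% / 28% | 40.0 − 14.4 = 25.6 points |
| 28% / 12% | 32.8 − 17.6 = 15.2 points |

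The same true effect gives coded differences from 15.2 to 25.6 points. Equal losses shrink it too.

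**Step 5: set against sampling error.** At 20% abstinent and 25 per arm, the standard error of the difference is √(2 × 0.20 × 0.80 / 25) = 0.113, so the 95% half-width is 1.96 × 0.113, about 22 points.

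**Step 6: completers alone are no cure.** Take a true 20% in both arms, all absent women smoking, and 3 v 7 lost. Completers show 0.20/0.88 = 22.7% v 0.20/0.72 = 27.8%, a false −5.1 points, while the planned rule gives 0. Neither analysis is right under both assumptions, which is why a range is needed.

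**The case against.** **The plan does look at attrition.** A reader might infer that nothing else is planned. That is too strong. Aim 2 compares attrition by arm and by abstinence status, which bears directly on this bias, and a mixed model is explored. What is missing is any alternative handling of missing abstinence for the effect size.

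**A false difference needs two conditions.** Attrition must differ between arms, and some absent women must be abstinent. With equal attrition and no effect the coded difference is exactly 0. The documents show no unequal attrition, and the design works against it: both arms have the same sessions, video schedule, reminder calls, tracking and gift cards. The extra $25 for the cotinine test goes to women who report abstinence, which gives abstainers more reason to be present and favours the case where the rule is right. All of this stands. It makes the bias less likely without excluding it, because retention can still differ by chance in arms of 25.

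**Sampling error is much larger.** True: 3.2 points against about 22. But the bias is systematic, and an interval that takes absent women as known smokers does not reflect it.

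**A later trial is not necessarily mis-sized.** A 20.4-point difference (36.4% v 16.0%) needs 72 per arm by the formula in Step 1, and it is tempting to say that the rule turns 52 into 72. The documents do not support calling that an error. Ordinary inflation for 20% loss already gives 52/0.8 = 65. If the later trial uses the same rule with similar retention, 20.4 points is the right planning difference. The protocol also does not say whether the 20.0% from the ongoing study already counts absent women as smoking; if it does, Step 4 deducts the loss twice.

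**The mixed model.** A reader might infer that a woman who misses month 2 and is cotinine-negative at month 3 is coded as smoking at month 2. The plan leaves this open: the coding sentence comes after the chi-square tests and before the mixed model, and does not say whether it covers both.

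**Conclusion.** The point holds in a limited form. One rule governs missing abstinence, nothing tests how far the effect size depends on it, and the rule is not conservative for the difference between arms. Under no effect, the false difference is 3.2 points at the documents' 20% and 4.8 at an assumed 30%, for 3 v 7 of 25 lost and absence unrelated to smoking. With the planning rates, an assumed 20% loss in both arms takes 25.5 points to 20.4. Every size quoted rests on assumed attrition. All of the bias disappears if every absent woman smokes. It is modest beside sampling error, and it matters because the estimate is meant to be reused. The documents do not show that the effect size will be wrong; they leave no way to see how much of it could be due to retention.

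**What to change.** In the SAP, Specific Aim 3:

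- Keep the planned rule as the main analysis, and report attrition by arm next to the effect size.
- Add one prespecified sensitivity analysis of the last abstinence outcome collected. With x women abstinent and m absent among the n in an arm, set the rate to (x + m·s)/n, where s is the share of absent women taken as abstinent. Let s run from 0 to the observed rate x/(n − m), separately in each arm. At s = 0 this is the planned analysis; at the upper end in both arms it is the completers result. Give the effect size with a 95% CI over a simple grid, and quote the range in later grant applications. Multiple imputation over many scenarios would be too heavy for arms of 25 with few women missing.
- State that missed visits enter the exploratory mixed model as missing and not as smoking.

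Separately, reconcile the timing. Aim 3 sets the effect size at 6 months, but the protocol's Research Design gives control women the SNC videos "right after the last follow-up assessment (3-month follow-up post-quit"), and Table 1 has no later visit. Read literally, no 6-month outcome exists to analyse.

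The cost is SAP wording and a short program, with no new data. The downside is a little more analysis and an effect size that looks less certain.
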